8.4.2 Analysis of Primary Endpoints

The analysis of the primary endpoints AUC_{0-t} and C_{max} of L-PZQ will be performed using the PK population. For the demonstration of bioequivalence different approaches will be applied for AUC_{0-t} and C_{max} . For AUC_{0-t} the standard approach will be followed, i.e. the point estimate and the 90% CI of the Test/Reference geometric mean ratio must fall within [0.80, 1.25]. AUC_{0-t} of L-PZQ will be log-transformed and analyzed using a generalized linear model as given by the SAS code below:

```
PROC GLM DATA=PK;
```

```
CLASS SEQ SUBJ PER TRT;
```

```
MODEL LNPARAM = SEQ PER TRT SUBJ(TRT) / DDFM=SATTERTH;
```

LSMEANS TRT / ADJUST=T PDIFF CL ALPHA=0.10.

TEST H=SEQ E=SUBJ(TRT);

RUN;

QUIT;

The treatment difference TEST – REFERENCE will be estimated, and the 90% CIs for the difference in LS-means will be calculated. The difference and 90% CIs will be back-transformed to the original scale. If the 90% CI for the ratio (test/reference) lies entirely within the interval [80.00 – 125.00], then the BE criterion is fulfilled for AUC_{0-t} .

For the analysis of C_{max} , a reference-scaled bioequivalence approach will be applied as follows:

Point estimate and 90% confidence interval will be computed as described above for AUC. If $CV_{WR} \leq 30\%$ for C_{max} (i.e. the within-subject CV for the reference drug is $\leq 30\%$), then the common acceptance range for bioequivalence will apply. For $30\% < CV_{WR} \leq 50\%$ the acceptance interval will be widened according to $[U, L] = \exp [\pm k \cdot sWR]$, where U is the upper limit of the acceptance range, L is the lower limit of the acceptance range, k is the regulatory constant set to 0.760 and sWR is the intrasubject standard deviation of the log-transformed values of C_{max} of the reference product. sWR will be calculated using the data under reference treatment only. For all values of CV_{WR} greater than 50% the acceptance range is fixed to [69.84 – 143.19].

The geometric mean ratio for C_{max} should always lie within [80.00 – 125.00].

- a. Descriptive statistics and boxplots will be provided by treatment.

CCI

PROC GLM DATA=PK;

CLASS SEQ SUBJ PER TRT GROUP;

MODEL LNPARAM = SEQ PER TRT GROUP GROUP*TRT SUBJ(TRT) / DDFM=SATTERTH;

LSMEANS TRT / ADJUST=T PDIFF CL ALPHA=0.10.

TEST H=SEQ E=SUBJ(TRT);

RUN;

QUIT;

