| 
Investigational Medicinal Product: dose/mode of administration/ dosing schedule Test: 1200 mg of Cisticid new formulation (two 600 mg tablets), single dose administered orally in fed condition
 |
| 
Reference: 1200 mg of Biltricide (two 600 mg tablets), single dose administered orally in fed condition in two periods.
 |
| 
Planned trial and treatment duration per subject: Screening period of maximal 28 days,
 |

Three weeks dosing period including washout followed by one week of clinical follow-up.

Statistical methods: Statistical analysis will be performed using the computer program package SAS® System PPD . If not stated otherwise, the level of statistical significance will be $\alpha=0.05$. PK data evaluation will be performed based on standard non-compartmental methods using the validated software tool PPD . Details on the statistical analysis and PK data analysis will be presented in the statistical analysis plan prior to database lock.

The statistical analysis will not be started until all data have been corrected and checked for plausibility and until all necessary coding and assessments have been completed.

The analysis of the primary endpoints AUC_{0-t} and C_{max} of L-PZQ will be performed using the PK population. Both parameters will be log-transformed before analysis. For the demonstration of bioequivalence different approaches will be applied for AUC_{0-t} and C_{max} . For AUC_{0-t} the standard approach will be followed, i.e. the point estimate and the 90% CI of the Test/Reference geometric mean ratio must fall within [0.80, 1.25]. A linear mixed-effects model will be applied for the analysis of AUC_{0-t} . The treatment difference TEST – REFERENCE will be estimated, and the 90% CIs for the difference will be calculated. The difference and 90% CIs will be back-transformed to the original scale. If the 90% CI for the ratio (test/reference) lies entirely within the interval [80.00 – 125.00], then the BE criterion is fulfilled for AUC_{0-t} .

For the analysis of C_{max} , a reference-scaled bioequivalence approach will be applied.

Substance Code
Protocol Number

Praziquantel
MS 200585-0002

Short title Praziquantel Bioequivalence Study

2 Sponsor, Investigators and Trial Administrative Structure

This clinical trial will be sponsored by:

Merck KGaA [name]

Committees

Ethics and Investigation
Committee :

PPD

Phone: PPD
Filing at PPD
PPD

Investigation Committee:

PPD

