5.1 Overall Trial Design and Plan

The purpose of the current relative bioavailability trial is to assess the bioequivalence (BE) of the the new 600 mg Cisticid tablet (Test) versus Biltricide (Reference) in healthy male volunteers under fed conditions.

This is a phase I, crossover, open-label, single dose, randomized, three period trial where subjects will be randomized to one of three sequences: T-R-R, R-T-R and R-R-T where T is test product and R is Reference product, with a washout period of at least 1 week in between.

The study will investigate the BE of the new 600 mg Cisticid tablet versus the comparator 600 mg tablet of Biltricide at a dose of 1200 mg (primary endpoints AUC_{0-t} and C_{max} of L-PZQ), administered in fed condition in 60 healthy male volunteers. Finally safety and tolerability will be also investigated.

In each treatment period subjects are institutionalized the evening before dosing until 24 hours after dosing with a washout period of 7 days. Total duration of the study for a subject is up to 7 weeks, including a Screening period of maximal 28 days, and 3 weeks dosing period including washout, and safety follow-up (EoT visit) at 7 days after third dose (period).

The subjects will be randomized to one of the 3 treatment sequences (see [Table 2](#) below).

Table 2 Treatment Sequences of the Study.

| Sequence | Period 1 | | Period 2 | | Period 3 | |
|----------|-----------|-----------------|-----------|-----------------|-----------|-------------------------------|
| 1 | Test | Wash-out 7 days | Reference | Wash-out 7 days | Reference | Wash-out 7 days and EOT visit |
| 2 | Reference | | Test | | Reference | |
| 3 | Reference | | Reference | | Test | |

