Descriptive statistical methods will be used to summarize demographic characteristics, pharmacokinetics parameters and adverse events. After the data base closing

Individual plasma concentration-time will be tabulated and plotted. Primary pharmacokinetics parameters, AUC and Cmax, will be tabulated and plotted by subject. Likewise, differences and odd ratios for test/reference will be tabulated for each subject for those parameters. Plasma concentration - time graphs will be made using arithmetic and semi-logarithmic scale. All de calculations will be determinated in concordance with NOM-177-SSA1-2013

Bioequivalence test methodology will be perform using the next codes: PRC GLM DATA=PK CLASS SEQ SUBJ PER TRT; MODELLNPARAM=SEQ PRE TRT SUBJ(TRT)/DDFM=SATTERTH; LSMEANS TRT/ADJUST=T PDIFF CL ALPHA=0.01. TEST H=SEQ E=SUBJ(TRT); RUN; QUIT;

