8.1 Interim Analysis

Bioequivalence for AUC:

A mixed model will be applied to log-transformed AUC0-t and AUC0-∞ with treatment, period and sequence as fixed effects, and subject (sequence) as a random effect. Based on the residual error term 90% confidence intervals will be computed for the estimated differences Test − Reference, resulting in 90% confidence intervals for the Test/Reference ratios after backtransformation.

Bioequivalence for Cmax:

The 90% confidence intervals will be computed for the estimated differences Test – Reference. If $CV_{WR} \leq 30$ the procedure to estimate is the same as the confidence intervals for AUC, if $30\% < CV_{WR} \leq 50\%$, the acceptance interval will be widened according to the next formula (U, L) = $\exp(\pm k'sWR)$, where U is the upper limit, L is the lower limit, k is the constant established as 0.760 and sWR is the intrasubject standard deviation for the Cmax log transformated value for reference product. For values greater than 50% the aceptace range going to be 69.84 – 143.19

TO evaluate the group effect, the next codes will be used: PROC GLM DATA=PK

CLASS SEQ SUBJ PER TRT GROUP;

MODEL LNPARAM=SEQ PER TRT GROUP GROUP*TRT SUBJ(TRT)/ DDFM=SATTERTH;

LSMEANS TRT/ ADJUST=T PDIFF CL ALPHA=0.10.

TEST H=SEQ E=SUBJ(TRT);

RUN;

QUIT;

Statistical analysis for secondary parameters

The secondary pharmacokinetics parameters (Tmax, AUCextrapolated, t½, Cl/F and Vd/F) going to be analyzed by descriptive statistics

9 Changes to the Planned Analyses in the Clinical Trial Protocol

The statistical methods as described in the protocol were adopted.

There are no changes to the planned analyses.

10 Protocol Deviations and Analysis Sets

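### The bioequivalence code nests subjects in treatment instead of sequence, so the width of the 90% CI does not respond to Test data

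*Protocol*

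**What the plan says.** Under Protocol 5.1, "subjects will be randomized to one of three sequences: T-R-R, R-T-R and R-R-T", so each subject contributes one Test and two Reference observations.

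Protocol 8.4.2 gives the AUC0-t model in PROC GLM as "MODEL LNPARAM = SEQ PER TRT SUBJ(TRT) / DDFM=SATTERTH". SUBJ(TRT) is also the error term in the TEST statement for sequence. For Cmax, "Point estimate and 90% confidence interval will be computed as described above for AUC", so the same code governs both primary endpoints. A second block, with dosing group added, reads "MODEL LNPARAM = SEQ PER TRT GROUP GROUP*TRT SUBJ(TRT) / DDFM=SATTERTH".

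SAP section 8 repeats the primary model as "MODELLNPARAM=SEQ PRE TRT SUBJ(TRT)/DDFM=SATTERTH", and SAP 8.1 repeats the group model. The subject term is therefore SUBJ(TRT) in all four code blocks.

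The prose differs. The Protocol synopsis says "A linear mixed-effects model will be applied for the analysis of" AUC0-t. SAP 8.1 specifies a mixed model "with treatment, period and sequence as fixed effects, and subject (sequence) as a random effect", with the interval based on the residual error. SAP section 9 reports no changes to the planned analyses, so the conflict is left open.

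**The concern.** Subject is nested in sequence and crossed with treatment. SUBJ(TRT) instead fits a separate parameter for each subject on each product. With one Test period per subject, each Test observation has its own parameter and leaves no residual. The error variance is then the Reference within-subject variance alone. That is the right quantity for sWR, which scales the Cmax limits, but the wrong one for the standard error of a Test–Reference difference.

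The stake is the pass/fail interval for a new formulation. If Test is more variable than Reference, or subjects differ in their Test/Reference ratio (subject-by-formulation interaction), the interval is too short and false equivalence becomes more likely. If neither is true, about half the residual degrees of freedom are lost for no gain.

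Three further faults follow from the same code:
- The adjusted test of sequence has nothing left to test.
- The group-by-treatment check fails in the same way.
- DDFM=SATTERTH is a PROC MIXED option that PROC GLM does not accept.

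**Working it through.** **Inputs.** From Protocol 8.1: AUC CV 39.5% for both products, true ratio 0.95, limits 0.80–1.25, one-sided alpha 0.05, 48 evaluable subjects, 20% dropout. Larger or smaller Test CVs and the interaction SD (sD) are assumptions made here.

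**1. The plan's own figure.** sWR² = ln(1 + 0.395²) = 0.1450. In the balanced design SE = √(1.5 × 0.1450 / 48) = 0.0673. With 2n − 3 = 93 degrees of freedom, power is 80.5% (77.9% at n = 45), and 48 / 0.8 = 60. The stated sample size reproduces, using the degrees of freedom of the subject-in-sequence model. With the coded 46 degrees of freedom, power is 79.9%.

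**2. Degrees of freedom at 16/16/16 (144 observations).**
- SUBJ(TRT): 96 subject-by-treatment cells + 2 for period = rank 98; residual 144 − 98 = 46.
- SUBJ(SEQ): 48 subjects + 2 for period + 1 for treatment = rank 51; residual 144 − 51 = 93.

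**3. Where the residual comes from.** Under SUBJ(TRT) every Test row has leverage 1. In a simulated data set, multiplying the Test noise by 5 left the mean square (0.9945) and SE (0.1763) unchanged. Under SUBJ(SEQ) the same change moved the mean square from 1.28 to 14.22 and the SE from 0.200 to 0.667. Test rows supply about 33% of the residual there.

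**4. What the SE estimates.** As coded, SE² estimates 1.5·sWR²/n. The true variance of the estimate is (sWT² + sWR²/2 + sD²)/n. Their ratio is r = (sWT² + sWR²/2 + sD²)/(1.5·sWR²). The one-sided error at the margin is close to P(t46 > 1.679/√r), and coverage is 1 − 2P.

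Example, Test CV 60%: sWT² = ln(1.36) = 0.3075, so r = (0.3075 + 0.0725)/0.2175 = 1.747 and √r = 1.322. Then 1.679/1.322 = 1.270, which gives an error of 10.5% and coverage of 79%.

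**5. Simulation** (n = 48, Reference CV 39.5%, 200,000 trials per row, true ratio 1.25). Each model cell gives 90% CI coverage / false-equivalence rate.

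| Test CV, sD | r | SUBJ(TRT) as coded | SUBJ(SEQ) |
|---|---|---|---|
| 39.5%, 0 | 1.00 | 90.0% / 5.0% | 90.1% / 5.0% |
| 34.5%, 0 | 0.85 | 92.5% / 3.8% | 91.3% / 4.4% |
| 45%, 0 | 1.18 | 87.3% / 6.3% | 88.8% / 5.6% |
| 50%, 0 | 1.36 | 84.5% / 7.7% | 87.6% / 6.2% |
| 60%, 0 | 1.75 | 79.0% / 10.5% | 85.7% / 7.1% |
| 39.5%, 0.20 | 1.18 | 87.1% / 6.5% | 88.6% / 5.7% |

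A separate run of 40,000 trials at ratio 0.80 with sD = 0.30 gave 8.3% as coded (coverage 83%) against 6.5%.

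**6. Other terms.**
- Dropping SEQ from the coded model leaves the rank at 98, so an adjusted sequence test has 0 degrees of freedom.
- Adding GROUP and GROUP*TRT raises the rank by 0 under SUBJ(TRT) and by 2 under SUBJ(SEQ).
- At 20/20/19 (one split of the 59 subjects in the SAP tables) or 17/16/15, the individual treatment LS-means are not estimable as coded. The Test–Reference difference still is.

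**The case against.** The strongest reply is that SAP 8.1 already describes the right model in words, the synopsis is compatible with it, and Protocol 8.4.1 defers detail to the SAP. On that reading there are two candidate models, and the fault is code that disagrees with correct prose. The code may also never produce the interval: PROC GLM would not accept it as printed, and SAP section 11 assigns the bioequivalence statistics to WinNonlin while section 8 names SAS.

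On size, the plan assumes equal CVs, and there the coded interval has nominal error. Every inflated figure needs a Test CV or interaction that the documents do not give, and a less variable Test makes the coded interval conservative. SUBJ(SEQ) with a pooled error is itself anti-conservative when Test is more variable, so only the difference between the two columns is due to the nesting. The point estimate still uses Test data, and the contrast remains estimable with unequal sequences. GROUP*TRT loses its degrees of freedom only in an adjusted test; fitted sequentially it keeps 2.

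All of these qualifications stand, but they do not settle the matter. The SAP that contains the correct sentence also prints the wrong code twice and declares no changes. Equal variance is a planning assumption, and a confirmatory interval should respond to the Test data if it fails.

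**Conclusion.** The concern holds. As coded, the width of the 90% CI for AUC0-t and Cmax does not depend on Test variability. This follows from the design and needs no assumption about the data. The consequence does depend on assumptions: about 0.6 points of power under equal variances, and a false-equivalence rate of 7.7% (Test CV 50%) to 10.5% (Test CV 60%), of which 1.5 (7.7 − 6.2) to 3.4 (10.5 − 7.1) points come from the nesting. Because code and prose prescribe different error terms for the deciding interval, the plan must be corrected before it can be called prespecified.

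**What to change.** Replace SUBJ(TRT) by SUBJ(SEQ) in the MODEL and TEST statements of the primary code in Protocol 8.4.2 and SAP section 8. In the group model (Protocol 8.4.2 and SAP 8.1) use SUBJ(SEQ*GROUP) in both statements, so that GROUP*TRT can be tested. Remove DDFM=SATTERTH from PROC GLM, or move to PROC MIXED with RANDOM SUBJ(SEQ), as the SAP 8.1 text describes. Name that one model as primary in the synopsis, Protocol 8.4.2 and SAP 8 and 8.1, and state which software produces the interval. Keep the Reference-only analysis for sWR.

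The cost is code and wording only; 48 evaluable and 60 randomized subjects remain adequate (80.5% power). The interval will tend to be wider than under the present code if Test proves more variable than Reference. Pooling the error leaves some inflation in that case, which the report should acknowledge.

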8.4.3 Analysis of Secondary Endpoints

All secondary endpoints will be listed and descriptively analyzed.

There will be no formal statistical comparison of the secondary PK endpoints. Treatment ratio and 90% confidence interval will be presented for AUC_{0-∞} of L-PZQ and for all the secondary PK endpoints for rac-PZQ (t_{max}, t_{lag}, AUC_{0-t}, AUC_{0-∞}, AUC_{extra}, C_{max}, t_{1/2}, λ_Z, CL/f and V_Z/f). For t_{max} the Hodges-Lehmann shift estimate will be calculated together with the 90% confidence interval according to Tukey.

8.4.4 Analysis of Safety and Other Endpoints

8.4.4.1 Safety endpoints

In general, for the evaluation of safety parameters, the numerical values will be summarized descriptively (N, arithmetic mean, median, standard deviation, minimum and maximum values). Categorical variables will be presented in frequency tables by the number of observations and percentages.

AE counts and subjects with AEs will be summarized for each treatment by system organ class and preferred term. In addition AEs will be tabulated and listed per subject and analyzed by severity and relationship to trial drug.

Subjects who prematurely withdrew from the trial or from treatment will be displayed in a by-subject listing, and summarized by primary withdrawal reason for each treatment sequence.

Safety laboratory parameters will be listed for each subject including changes from baseline and flags for measurements outside the reference ranges, where applicable. Laboratory parameters (hematology and clinical chemistry) will be summarized by time point including both absolute values and changes from baseline.

Vital signs and ECG parameters will be listed by subject including changes from baseline, and summarized by treatment and time point using descriptive statistics. Physical examination assessments will be listed for each subject.

8.4.4.2 Further endpoints

Demographic parameters (such as age, height, weight) and other baseline characteristics will be summarized by means of tabulated descriptive statistics for all subjects by sequence group and overall. Subject habits (including alcohol consumption and smoking history), medical history, prior and concomitant medications and exposure to IMP will be listed for each subject.

L-PZQ and rac-PZQ concentrations will be listed by subject, by treatment, by period and time point for each treatment and summarized by treatment and time point. Individual and mean concentration versus time plots will be prepared.

Further details will be described in the statistical analysis plan.

8.5 Interim and Additional Planned Analyses

No interim analysis is planned.

8.6 Deviation and Exclusion to the Statistical Analysis

All deviations should be justified with statistical or scientific data and any change to the original statistical plan should be documented, in the study master file and in the pharmacokinetics statistical report as well as in the final study report. Subjects' data will not be replaced. Any missing data will be considered as non-existent data. Likewise, data cannot be removed from the statistical analysis, except in the following events.

9.1 Responsibilities of the Investigator

The Principal Investigator is responsible for the study conduct at the site. She will make sure that the study is conducted according to the clinical trial protocol, ethical principles established in the Declaration of Helsinki, ICH, GCP and established regulation NOM-177-SSA1-2013 (28), which states tests and procedures to show that a drug is interchangeable as well as the requirements which Authorized Third-Parties should fulfill to perform the tests. The Investigator should ensure that only subjects who have provided their informed consent are included in the study.

9.2 Subject Information and Informed Consent

An unconditional requirement for each subject before their participation in the study is to have a written informed consent, which should be given before any study-related activity is carried out.

Therefore, the Principal Investigator or designated personnel should provide appropriate information before obtaining informed consent.

Subject's Information Sheet should be elaborated in Spanish, according to the ICH GCP and will be provided by the Sponsor with the purpose to get the informed consent. Besides providing written information to the potential subject, Investigator or designated person will inform them verbally all relevant aspects of the study, using language chosen so that information can be fully and easily understood by the subjects. Subject will be given enough time to read the information and ask questions and request additional information and explanations.

After providing information to the subject, informed consent form should be signed and dated by the subject, the Principal Investigator or designated personnel and two witnesses.

The dated and signed informed consent will be kept in the study site and should be securely filed so that files can be retrieved at any moment for monitoring, auditing and inspection purposes. A copy of the signed and dated informed consent form should be provided to the subject before their participation in the study.

Whenever new relevant information arises for the informed consent, the Investigator will revise subject's information and any other written information to be provided to the subjects, which should be submitted to the Committees for review and approval.

Revised and approved version of the written information will be used. The Principal Investigator or designated personnel will explain each subject all changes made to the previous version and will obtain a new written consent to continue his participation in the study. Subject will be given enough time to read the information and ask questions, and request additional information and explanations about changes.

9.3 Subject Identification and Privacy

A unique number is assigned to each subject that corresponds to their clinical file number, this number will be used as subject's identification in the study, as well as in the clinical study database. Once it is confirmed that all inclusion criteria and none exclusion criteria have been met, a consecutive number in ascendant order will be assigned to subjects. For each one of these numbers, it will correspond one of the three sequences as described in section 6.3.

All data collected from study subjects will be recorded in appropriate charts. Only the Investigator will be able to link the test's data for a subject by means of an identification list which will be located at the site. For each subject, clinical data will be available for verification

purposes by the monitor, audits and regulatory inspections, but subject's confidentiality will be strictly kept.

Data protection and confidentiality will be kept during data entry, processing, submission and storage. Subjects will be informed about it and they will be requested to provide their consent for data management according to the national regulations.

The Ministry of Health, Ethics and Investigation Committee and the Investigational Committee will be the only authorized bodies for reviewing study documentation, (which includes participant subject's identity data) and documents considered confidential by PPD [REDACTED] and by the analytical unit from Merck.

